1 INTRODUCTION

1.1 Background Information

The current commercially available mechanical mitral valves range in sizes from 16mm to 37mm. The mitral annulus in young pediatric patients can range from 12mm to 30mm with a mean of 18mm.¹ A mitral valve annulus will typically require a sewing diameter of approximately 2mm larger than the valve size. As a 16mm valve is currently the smallest diameter valve on the market there is a portion of the pediatric population that would benefit from the availability of a smaller diameter valve.

Evidence exists to suggest that oversized valves are associated with increased mortality and morbidity rates particularly in the very young patient population.¹⁻⁴ A small mitral annulus can rarely be enlarged to accept a prosthesis larger than its diameter.⁵ Intraoperative problems associated with implantation of a mitral prosthesis too large for the size of the annulus include damage to the conductive system, obstruction of the left ventricular outflow tract (LVOT), impairment of valve mobility, and damage to the left circumflex artery.^{2,6} The need for pacemaker insertion after mitral valve replacement due to interruption of the conduction system of the heart has been estimated at 5-16%.^{1,3-7} Mismatch of the annulus size and the prosthesis can also lead to mitral stenosis necessitating a second valve replacement procedure.^{5,8,9}

1.2 Disease to be Treated

Mitral valve disease can be the result of congenital valve anomalies such as mitral stenosis, mitral insufficiency and complete or partial atrioventricular canal. Other causes of mitral valve disease include endocarditis, rheumatic heart disease, and mitral insufficiency associated with Marfan syndrome.^{5,10} Approximately half of pediatric patients requiring mitral valve replacement have previously had valvuloplasty or valvulotomy to repair the diseased valve.^{4-7,10,11}

1.3 Current Treatment Options

Surgical reconstruction to repair the mitral valve is the optimal treatment in the pediatric population. Surgical repair can in some cases eliminate the need for future mitral valve replacement and in other cases postpone it.^{2,4,7,11} The pulmonary autograft technique described by Ross and Yacoub and modified by Kabbani has shown promise in those patients with mitral valves that have an effective orifice area of at least 3cm².^{5,7}

When the mitral valve cannot be repaired surgically the only remaining treatment option is replacement with a prosthetic valve.⁷ A second and sometimes third valve replacement after initial mitral valve replacement is expected in the very young pediatric population. The rate of mitral valve re-operation reported in the literature for patients younger than five years of age is approximately 40%.^{4,7,10,11}

Mechanical valves are generally chosen over bioprosthetic valves when a very small size is required because they exhibit better hemodynamic characteristics than bioprostheses.⁵ Valve replacement with allografts and xenografts are reported to show poor durability in pediatric patients.⁵ In addition, the rate of premature calcification observed with bioprostheses appears to be high in this population.^{2,7,8,11}

2 INVESTIGATIONAL DEVICE

2.1 Device Name

SJM™ Masters HP™ 15mm Rotatable Mechanical Heart Valve (15mm MHV).

2.2 Device Description

The investigational device is a 15mm, rotatable, bileaflet mechanical heart valve designed for implantation in the mitral position. This valve is part of the SJM™ Masters HP™ Series product line. The Hemodynamic Plus (HP) model has been designed to maximize effective orifice area. This is made possible by removing the sewing cuff from the annulus.

2.3 Intended Use

The 15mm MHV is intended for use as a replacement mitral valve in patients five years or less of age with a diseased, damaged, or malfunctioning mitral valve. This device may also be used to replace a previously implanted prosthetic mitral heart valve.

3 STUDY DESIGN

The study is a single arm, prospective, non-randomized, multi-center clinical investigation.

3.1 Study Duration

Each enrolled subject will be assessed at baseline, procedure, post-procedure, 30 days, six months, 12 months, and annually thereafter for as long as the valve remains implanted. Each enrolled subject will be followed for five years from the date of implant, until subject withdrawal, or until study closure, whichever occurs earliest.

4 STUDY PURPOSE AND OBJECTIVE

4.1 Purpose

The purpose of the study is to provide evidence of safety and effectiveness to support a supplement to the St. Jude Medical Masters Series PMA (P810002) for approval of the 15mm MHV.

The rationale for this study is to offer a replacement mitral valve for patients with anatomy that is too small for the currently commercially available valves ranging in size from 16mm to 37mm.

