4.2 Objective

The objective of this study is to evaluate the safety and effectiveness of the 15mm MHV in subjects five years or less of age with a diseased, damaged, or malfunctioning mitral heart valve. The objective will be evaluated by assessing valve-related adverse events, subject survival, subject growth, and echocardiogram assessment of hemodynamic function through the five year follow-up visit as long as the valve remains implanted.

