5 ENDPOINTS

5.1 Primary Safety Endpoint

The primary safety endpoint for this study is the actuarial (Kaplan-Meier) rate of total valve-related adverse events experienced through 365 days post implant or until the valve is removed/replaced due to anatomical growth of the subject, whichever occurs first. Valve-related adverse events to be evaluated are:

- Death
- Endocarditis
- Hemorrhage (whether or not due to anticoagulant/antiplatelet medication) [all and serious]
- Nonstructural dysfunction (including perivalvular leak [all and serious], hemolysis, and hemolytic anemia)
- Reoperation (including valve explant, not due to anatomical growth of the subject) [all and valve-related]
- Structural valve deterioration
- Thromboembolism
- Valvular thrombosis

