5.2 Primary Effectiveness Endpoints

The primary effectiveness endpoints in this study include the following:

1. Survival at 12 months post implant or survival until the valve is removed/replaced due to anatomical growth of the subject, whichever occurs first.
2. Peak gradient as assessed by echocardiography at 12 months post implant or when the valve is removed/replaced due to anatomical growth of the subject, whichever occurs first.
3. Mean gradient as assessed by echocardiography at 12 months post implant or when the valve is removed/replaced due to anatomical growth of the subject, whichever occurs first.

4. Valvular regurgitation as assessed by echocardiography at 12 months post implant or when the valve is removed/replaced due to anatomical growth of the subject, whichever occurs first.

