6 STATISTICAL ANALYSIS

6.1 Statistical Analysis and Reporting

Kaplan-Meier adverse event rates with 95% confidence intervals and early rates will be calculated for all safety and survival endpoints.

Hemodynamic function will also be evaluated at each visit for each of the following variables:

- Mean pressure gradients across the mitral valve
- Peak pressure gradients across the mitral valve
- Cardiac output
- Cardiac index
- Valvular regurgitation (and the site, as appropriate)

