7.2 Potential Risks

Potential risks of receiving a mechanical mitral valve include:

- The need for a second valve replacement due to either dehiscence, valve failure or malfunction, development of mitral stenosis, unacceptable hemodynamic status or eventual somatic outgrowth.
- Heart failure requiring cardiac transplant.
- Cardiac arrhythmia with or without the need of pacemaker implantation.
- Hemolysis potentially resulting in anemia with or without splenomegaly and/or development of cholelithiasis.
- Infection including but not limited to endocarditis, myocarditis, cellulitis and/or septicemia.
- Thromboembolism or hemorrhage causing stroke, myocardial infarction or other significant impairment.
- Obstruction or distortion of adjacent cardiac structures.

All of the identified risks have the potential to result in death. The mortality rate reported for mitral valve replacement in the pediatric population is highly variable and ranges between approximately 5 and 30%.^{3,7,12-15}

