11 ECHOCARDIOGRAPHY PROCEDURES

Hemodynamic function will be evaluated by calculating the number of observations, mean, standard deviation, minimum and maximum values for each of the following variables:

- Mean pressure gradients across the mitral valve
- Peak pressure gradients across the mitral valve
- Cardiac output
- Cardiac index
- Valvular regurgitation

Transthoracic echocardiogram (TTE) examinations are required for each subject at baseline, post-procedure, 30 days, 6 months, 12 months, and annually thereafter for as long as the valve remains implanted.

The study specifies TTE rather than transesophageal echocardiography (TEE) to minimize subject risk. Echocardiographic data collected from TEE warranted for any other medical purpose is allowed.

For Adjunctive EU/CU Subjects, echocardiograms should be collected from subject's medical records, when available, for visits conducted prior to enrollment. Additionally, echocardiograms should be collected even if any echocardiographic assessments occurred outside of a specified visit window as they may be used as supporting source documentation on the subject.

CDs of the echocardiography exams from each required visit will be forwarded to the echocardiography core laboratory (core lab) for interpretation. The primary responsibility of the core lab is to provide consistent interpretation of TTE data across all study sites by completing the TTE Case Report Form (CRF).

The sponsor will use only the measurements from the core lab for analysis. If the core lab determines the echocardiogram is unreadable, the subject may be asked to return for another echocardiogram.

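### The stated purpose is evidential, but no primary endpoint has a benchmark and three of five have no planned interval, so the plan supports estimation only

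*Combined protocol and SAP*

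**What the plan says.** Section 3 sets the design: "The study is a single arm, prospective, non-randomized, multi-center clinical investigation". Section 4.1 says the study is to "provide evidence of safety and effectiveness to support a supplement" for the 15mm valve. Section 4.2 is milder: "The objective of this study is to evaluate the safety and effectiveness of the 15mm MHV".

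There are five primary endpoints. Section 5.1 has one for safety, "the actuarial (Kaplan-Meier) rate of total valve-related adverse events experienced through 365 days post implant". Section 5.2 has four for effectiveness. The first is "Survival at 12 months post implant or survival until the valve is removed/replaced due to anatomical growth of the subject"; the others are peak gradient, mean gradient and valvular regurgitation on echocardiography at 12 months. Each of the five can end earlier if the child outgrows the valve.

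In the supplied text, section 6 consists of 6.1 alone. It states that "Kaplan-Meier adverse event rates with 95% confidence intervals and early rates will be calculated for all safety and survival endpoints", and that hemodynamic variables will be evaluated at each visit. Section 11 says how: by the "number of observations, mean, standard deviation, minimum and maximum values" of each variable, with regurgitation on the same list as the gradients. It also says that only core-lab measurements will be analysed.

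The only mortality figure is in section 7.2, under potential risks. The rate reported in the literature for children is described as "highly variable and ranges between approximately 5 and 30" percent.

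**The concern.** Without a concurrent control, a conclusion about safety or effectiveness needs something outside the study to compare with. No target rate, acceptable gradient, acceptable regurgitation grade, historical comparator or hypothesis is attached to any primary endpoint. The purpose in 4.1 promises more than the analysis delivers, and the standard for judging the results would be settled after they are known.

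The second gap is narrower. For the three echocardiographic endpoints, the planned output does not show how precise the estimates are. For regurgitation it may not even show how many children had each grade. In a study of a valve for very small children the numbers may be low, so a reader needs to see the uncertainty.

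**Working it through.** **1. The five primary endpoints against the planned analysis (sections 5.1, 5.2, 6.1 and 11)**

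| Primary endpoint | Benchmark or rule | 95% interval planned |
|---|---|---|
| Valve-related event rate to 365 days | none | yes (6.1) |
| Survival at 12 months | none | yes (6.1) |
| Peak gradient at 12 months | none | no |
| Mean gradient at 12 months | none | no |
| Regurgitation at 12 months | none | no |

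That is 0 of 5 with a benchmark, 2 of 5 with an interval and 3 of 5 without. The closest thing to a decision criterion is in section 15.3, where the DSMB is to set termination guidelines. Those have no figures and concern stopping, not success.

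**2. Size of the missing interval for a gradient.** The plan has no figure of its own to reproduce, and the supplied text states no sample size. The values of n below are assumptions. The half-width of a 95% t-interval, in SD units, is t(0.975, n−1)/√n:

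- n = 10: 2.262/3.162 = 0.72
- n = 15: 2.145/3.873 = 0.55
- n = 20: 2.093/4.472 = 0.47
- n = 30: 2.045/5.477 = 0.37
- n = 50: 2.010/7.071 = 0.28

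**3. Size of the missing interval for a regurgitation grade.** For x children in a grade out of n, the exact (Clopper-Pearson) limits are the 2.5% quantile of Beta(x, n−x+1) and the 97.5% quantile of Beta(x+1, n−x). The counts are illustrative:

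- 0 of 10: 0% to 30.8%
- 1 of 20: 0.1% to 24.9%
- 3 of 20: 3.2% to 37.9%
- 6 of 20: 11.9% to 54.3%

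None in 10 with a given grade is thus still compatible with a true proportion of about 31%. A mean and SD would not show this.

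**4. What no benchmark means where an interval is planned.** Read the same limits as 12-month mortality, with a binomial interval standing in for the Kaplan-Meier one. One death in 20 (5%) gives 0.1% to 24.9%, and six in 20 (30%) give 11.9% to 54.3%. The intervals overlap between 11.9% and 24.9%, and the plan attaches no conclusion to either.

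**5. What a 30% mortality bar would do.** Suppose the upper exact limit had to lie below the top of the range in 7.2. The most deaths allowed, and the probability of meeting the bar at an assumed true mortality of 15%, are:

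- n = 20: at most 1 death (upper limit 24.9%; 2 deaths give 31.7%). Met with probability 18%, missed 82%.
- n = 30: at most 3 deaths (26.5%; 4 give 30.7%). Met 32%, missed 68%.
- n = 50: at most 8 deaths (29.1%; 9 give 31.4%). Met 67%, missed 33%.

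**The case against.** The best defence is that a small pediatric device study is properly descriptive. Section 4.2 speaks of evaluating, section 4.1 of supporting a submission, and the regulator makes the judgement. On that view estimates are the right output and no rule is needed. Most of this stands, and it is why the remedy is to match the stated purpose to an estimation plan and not to add a hypothesis test.

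The defence also notes that a t-interval follows directly from the count, mean and SD that section 11 already reports. That is true for the gradients, where the gap is one of reporting. It does not help with regurgitation: if that is graded, proportions and their intervals cannot in general be recovered from a mean and SD. The supplied text names no grading scale, though the core-lab form, which is not reproduced, may do so.

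Three stronger readings are tempting, and the documents do not support them.

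- *Any result would support the claim.* A plan with no rule returns estimates, not automatic support. What can be said is that no result is prespecified as failing to support the purpose.
- *The trial cannot answer its question.* The question in 4.2 is one of evaluation, and rates with intervals do answer it for safety and survival. Those intervals would also show imprecision.
- *The range in 7.2 is the sponsor's benchmark, so 30% should be the bar.* It is risk background for children generally, not limited to this age group, and it has no stated time horizon. It would cover one endpoint of five and leave the safety endpoint without a rule. Section 15.2.2 places pivotal enrolment under Revisions A or B, and section 9.6 already draws on experience with enrolled subjects, so a bar set now could follow knowledge of outcomes.

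**Conclusion.** The concern holds as a mismatch between purpose and analysis. All five primary endpoints lack a prespecified benchmark, so the plan supports estimation only. Three of the five also lack an interval, and the summary prescribed for regurgitation is a poor one if it is recorded as a grade.

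The counts (0 of 5 with a benchmark, 3 of 5 without an interval) come directly from the text. The sizes do not: they rest on assumed samples of 10 to 50 and on binomial intervals that ignore follow-up ending at growth-related explant. They show the order of magnitude, which is roughly 0.3 to 0.7 SD of unreported uncertainty in an average gradient. The data remain usable. This is an inexpensive improvement to reporting and wording, not a defect that invalidates the study.

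**What to change.** - **Sections 6.1 and 11, gradients.** Add a 95% t-interval for peak and for mean gradient at 12 months, and give the number of children with a core-lab reading. Keep the existing descriptive statistics.
- **Sections 6.1 and 11, regurgitation.** Name the core-lab grading scale. Report the number and proportion of children in each grade at 12 months with exact 95% intervals, in place of the mean and SD.
- **Sections 4.1 and 4.2.** State that the study estimates event rates, survival and hemodynamic values, and that conclusions are limited to the estimates and their intervals.
- **No mortality success rule.** Leave the range in 7.2 as risk background.

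This needs no new patients, visits or data. The cost is a few sentences, a little more analysis and a more modest stated purpose.

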4.2 Objective

The objective of this study is to evaluate the safety and effectiveness of the 15mm MHV in subjects five years or less of age with a diseased, damaged, or malfunctioning mitral heart valve. The objective will be evaluated by assessing valve-related adverse events, subject survival, subject growth, and echocardiogram assessment of hemodynamic function through the five year follow-up visit as long as the valve remains implanted.

5 ENDPOINTS

5.1 Primary Safety Endpoint

The primary safety endpoint for this study is the actuarial (Kaplan-Meier) rate of total valve-related adverse events experienced through 365 days post implant or until the valve is removed/replaced due to anatomical growth of the subject, whichever occurs first. Valve-related adverse events to be evaluated are:

- Death
- Endocarditis
- Hemorrhage (whether or not due to anticoagulant/antiplatelet medication) [all and serious]
- Nonstructural dysfunction (including perivalvular leak [all and serious], hemolysis, and hemolytic anemia)
- Reoperation (including valve explant, not due to anatomical growth of the subject) [all and valve-related]
- Structural valve deterioration
- Thromboembolism
- Valvular thrombosis

5.2 Primary Effectiveness Endpoints

The primary effectiveness endpoints in this study include the following:

1. Survival at 12 months post implant or survival until the valve is removed/replaced due to anatomical growth of the subject, whichever occurs first.
2. Peak gradient as assessed by echocardiography at 12 months post implant or when the valve is removed/replaced due to anatomical growth of the subject, whichever occurs first.
3. Mean gradient as assessed by echocardiography at 12 months post implant or when the valve is removed/replaced due to anatomical growth of the subject, whichever occurs first.

4. Valvular regurgitation as assessed by echocardiography at 12 months post implant or when the valve is removed/replaced due to anatomical growth of the subject, whichever occurs first.

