9.2 Assessment Schedule

All enrolled subjects will be assessed according to the following schedule for as long as the valve is implanted.

Table 1: Assessment Schedule

ASSESSMENTS	Baseline	Procedure	Post-Procedure ¹ (+ 24 hours)	30 Days ¹ (± 14 days)	6 Months ¹ (± 30 days)	12 Months ¹ (± 60 days)	Annual Visits through 60 Months ¹ (± 60 days)	Explant (Prior to procedure)
Medical History	X							
Physical Exam (PE)	X		X	X	X	X	X	X
Transthoracic Echocardiogram (TTE) ²	X		X	X	X	X	X	X
Blood Collection ³	X		X	X	X	X	X	X
Anticoagulant/Antiplatelet Medication Collection	X	X	X	X	X	X	X	X
Adverse Event Collection ⁴		X	X	X	X	X	X	X
Adverse Event Follow-up ⁵			X	X	X	X	X	X

1. Visits are to occur as long as the valve remains implanted.
2. The study specifies TTE rather than transesophageal echocardiography (TEE) to minimize subject risk. Echocardiographic data collected from TEE warranted for any other medical purpose is allowed.
3. Plasma free hemoglobin for hemolysis evaluation. Spot urine urobilinogen is an acceptable alternative if a non-hemolyzed blood sample cannot be obtained.
4. Refer to section 15.2 for a list of adverse events that are required to be collected and reported.
5. Required only for subjects who have an unresolved adverse event.

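### The primary gradient and regurgitation endpoints take no value from a valve explanted before its 12-month echo for a reason other than growth, although an echo before explant is scheduled

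*Combined protocol and SAP*

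**What the plan says.** Items 2, 3 and 4 of Section 5.2 are peak gradient, mean gradient and valvular regurgitation. Each has the same two possible assessment times, and the earlier one applies. For item 3 they are "Mean gradient as assessed by echocardiography at 12 months post implant or when the valve is removed/replaced due to anatomical growth of the subject". Section 5.1 foresees explant for other reasons, because it counts such explants under reoperation in the primary safety endpoint. Section 5.2 gives them no assessment time.

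Four other places bear on this:

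- **Section 9.2, Table 1.** Note 1 says "Visits are to occur as long as the valve remains implanted". The 12-month visit has a window of ±60 days. A separate explant column, to be completed before the operation, has the transthoracic echo (TTE) marked and is not limited by reason for explant.
- **Section 6.1.** Hemodynamic function is also evaluated visit by visit. The section does not say whether the explant echo is one of those visits or whether it feeds the primary endpoints.
- **Section 11.** Hemodynamics are summarised by "calculating the number of observations, mean, standard deviation, minimum and maximum values". TTEs are "required for each subject at baseline, post-procedure, 30 days, 6 months, 12 months, and annually thereafter", a list that leaves out the explant echo. Exams from required visits go to the core laboratory, and only core-lab measurements are analysed.
- **Section 7.2.** The reasons given for a second replacement include "development of mitral stenosis, unacceptable hemodynamic status or eventual somatic outgrowth".

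**The concern.** Two children may both lose the valve at, say, eight months, each with a TTE just before surgery. If the reason is growth, that echo is the primary value. If the reason is obstruction or leak, the echo is not used, and no 12-month value can arise later because visits end with the valve.

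The reason for removal therefore decides whether a valve is in the primary summary, and some of those reasons are the property being summarised. Besides the reasons in Section 7.2, Appendix 11 describes nonstructural dysfunction (pannus entrapment and paravalvular leak are among its examples) and valvular thrombosis that obstructs flow or impairs function. Where such valves are removed early, the remaining valves will tend to show lower gradients and less regurgitation than all implanted valves would. The maximum is especially exposed, since losing one valve can change it.

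Section 4.1 says the study is to support a PMA supplement, so a reader of the 12-month hemodynamic results needs to know which valves they describe.

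**Working it through.** The supplied text gives no planned figure for these endpoints, so there is none to reproduce. The check has two parts.

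**1. Which valves give a primary echo value**

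- In place at 12 months, working well or badly: one value per endpoint.
- Removed earlier for growth: one value, at removal.
- Removed for another reason before the 12-month echo: no value.

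The 12-month window runs from 365 − 60 = day 305 to 365 + 60 = day 425. A pre-explant TTE inside it could arguably serve as the 12-month echo. The gap is therefore clear only for explants before about day 305.

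**2. How far the summaries could move**

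Let m be the mean gradient in the valves that now contribute. Let p be the share of the enlarged set made up of non-growth explants with a usable pre-explant echo, and d their excess mean gradient. Then

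mean with them − mean without them = [(1 − p)m + p(m + d)] − m = p × d.

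Both p and d are assumptions; the documents give neither.

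| p | d = 0 | d = 2 mmHg | d = 5 mmHg | d = 10 mmHg |
|---|---|---|---|---|
| 5% | 0 | 0.10 | 0.25 | 0.50 |
| 10% | 0 | 0.20 | 0.50 | 1.00 |
| 20% | 0 | 0.40 | 1.00 | 2.00 |

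Echo availability matters. Take 100 implanted valves, 10 of them non-growth explants, with the other 90 all contributing and d = 5 mmHg:

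- All 10 echoes usable: p = 10/100, shift 0.50 mmHg.
- Five usable: p = 5/95 = 5.3%, shift 0.26 mmHg.
- None usable: no shift.

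For regurgitation, suppose it is reported as the proportion above some grade, which is my choice for illustration. The proportion over all valves is (1 − p) × (proportion in contributing valves) + p × (proportion in explanted valves). Assume 10% in contributing valves and 30% to 80% in explanted valves:

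- p = 5%: 0.095 + 0.015 = 11.0% to 0.095 + 0.040 = 13.5%.
- p = 10%: 0.09 + 0.03 = 12% to 0.09 + 0.08 = 17%.
- p = 20%: 0.08 + 0.06 = 14% to 0.08 + 0.16 = 24%.

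**The case against.** The strongest defence is that the rule is coherent. A removed valve has no 12-month gradient. The plan describes function in valves still in place and counts a non-growth removal as a safety failure. Section 5.1 captures the explant, and also the nonstructural dysfunction or thrombosis behind it. Section 6.1 still summarises the earlier visits these children reached, and its by-visit wording could be read to include the explant assessment. A pre-operative echo in an unstable child is also not the same measurement as a routine 12-month echo.

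Much of this stands. The events are not lost to the trial, and it is a good reason to leave the endpoint definition alone. But a count of safety events does not correct a mean, a maximum or a regurgitation summary. The growth rule already mixes time points. The objective in Section 4.2, "echocardiogram assessment of hemodynamic function through the five year follow-up visit as long as the valve remains implanted", is no bar either, because the explant echo is taken while the valve is still in. Whether that echo enters any summary is at best ambiguous, since the Section 11 list omits it.

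A reader might go further and infer that failing valves in general are excluded. They are not: a dysfunctional valve still in place at 12 months contributes. Nor is every early explant informative. Appendix 11 allows for removal because of noise or recall, or as a prophylactic measure, where the effect on gradients may be near zero.

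**Conclusion.** The gap is real on the text. Before about day 305, a non-growth explant gives no value to endpoints 2 to 4, and for some explants the reason may be the hemodynamic property itself. Where that is so, the primary mean, maximum and regurgitation summaries will tend to look too favourable.

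The size is unknown. Over the assumed ranges the mean gradient shifts by 0 to 2.0 mmHg, and by zero if the excluded valves were no worse. A reader might take the re-operation rate of about 40% in Section 1.3 as a guide to the share lost. It is not one: the figure is not split by reason for re-operation and has no time window, so it gives no rate of non-growth explant within the first year.

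A reader might also infer that a success criterion or error rate is compromised. The supplied text sets no target, comparison or test for these endpoints, so the effect is confined to how a descriptive result is read. The improvement is cheap and worth making, but the study does not depend on it.

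**What to change.** Leave Section 5.2 unchanged and make three text changes:

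1. **Supportive analysis (Section 6.1).** Repeat endpoints 2 to 4 using the core-lab pre-explant echo for any explant before the 12-month echo, whatever the reason, and show growth and non-growth explants separately. Date it to the revision that adds it. Section 15.2.2 refers to pivotal subjects enrolled under Revisions A or B, so it should not be called prespecified for them.
2. **Accounting (Section 6.1).** For each endpoint, report the number contributing over the number implanted, with the reason for each missing value: non-growth explant, death, withdrawal, missed or unreadable echo, or no pre-explant echo.
3. **Reconciliation (Section 11).** Align its list of TTE visits with the explant column of Table 1, so that these echoes clearly go to the core lab.

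No new test is needed, because Table 1 already schedules the echo. The cost is an amendment reviewed under Section 17.1.2. On the downside, the supportive means may be less favourable and will mix time points. Some explants will have no usable echo, particularly emergencies and EU/CU subjects, whose earlier data come from medical records only where these exist.
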